#### **6.3.3.5      *Percentages of Subjects with Migraine Days and Headache Days Over Time in the First Week on DBT***

Analyses are based on the first week EOD treated migraine analysis set, i.e., subjects in the DBT efficacy analysis set with (1)  $\geq 24$  days of eDiary efficacy data (not necessarily consecutive) in the OP analysis period, (2) 7 consecutive days of eDiary efficacy data in the first week (i.e., study days 1 through 7) of the on-DBT efficacy analysis period, and (3) EOD dosing in the first week of the on-DBT efficacy analysis period, defined as all 4 study days 1, 3, 5, and 7 being study drug dosing days and all 3 study days 2, 4, and 6 not being study drug dosing days (see Section 9.5).

## Treatment Group Comparisons

Analyses are based on the first week EOD migraine analysis set with eDiary efficacy data dates in the OP and on-DBT efficacy analysis periods (see Section 7.2).

For each pain intensity (total; moderate or severe), the percentages of subjects with a migraine day are compared between rimegepant and placebo at study days 1 through 7 of the DBT Phase using Mantel-Haenszel risk estimation with stratification by 4-level randomization stratum. Percentages are calculated against the number of subjects in the first week EOD treated migraine analysis set at all time points.

The table displays the following statistics at study days 1 through 7 by headache pain intensity:

- Response rate (i.e., “n/N” and percentage), ASE, and 95% CI for each treatment group
- Stratified percentage difference between rimegepant and placebo (rimegepant – placebo), ASE, 95% CI, and p-value.

The table also summarizes the percentage of migraine days by headache pain intensity (total; moderate or severe) in the OP descriptively as a continuous variable as a baseline reference. For each subject, the percentage is calculated as  $100 \times (\text{total number of migraine days in the OP analysis period}) / (\text{total number of eDiary efficacy data days in the OP analysis period})$ .

All analyses described above are performed analogously for headache days.

### Results support exploratory objective #5.

#### **6.3.3.6      *Time to Percentage Reduction From OP in Number of Migraine Days and Number of Headache Days per Month Over Time on DBT***

The following time-to-event endpoints are assessed by headache pain intensity (total; moderate or severe) for the migraine analysis set:

- 1) Time to  $\geq 30\%$  reduction from the OP in the number of migraine days per month
- 2) Time to  $\geq 50\%$  reduction from the OP in the number of migraine days per month.

Each time-to-event endpoint is assessed by headache pain intensity using a time-to-event distribution summary table presenting the following statistics: number and percentage of subjects with events; number and percentage of subjects censored; time to event median with 95% CI and quartiles, where the 95% CI for the median is estimated using the method of Brookmeyer and Crowley.

Each time-to-event endpoint is also assessed using a Cox proportional hazards model with the following variables: age, sex, race, 4-level randomization stratum, and treatment group. Race may be reduced to fewer levels (e.g., white versus non-white) based on the availability of data. The hazard ratio estimate (rimegepant versus placebo), 95% CI, and p-value are reported.

For a given time-to-event endpoint, subjects are considered to have an event through Month 3 based on the first month that they are evaluable and the endpoint is achieved. Otherwise, subjects

who do not have an event through Month 3 are censored at the last month they are evaluable. Subjects must have  $\geq 14$  days of eDiary efficacy data (not necessarily consecutive) in a month to be evaluable at that month.

All analyses described above are performed analogously for headache days per month.

Results support exploratory objective #6.

#### **6.3.3.7      *Acute Migraine Medication Days per Month Over Time on DBT***

Acute migraine medication days per month are assessed analogously to acute migraine-specific medication days per month (see Section 6.3.2.2).

An acute migraine medication day is defined in Section 9.2.3.

Analyses are based on the migraine analysis set with eDiary efficacy data dates in the on-DBT efficacy analysis period.

The number of acute migraine medication days per month in the DBT Phase are prorated to 28 days.

### **Descriptive Analyses**

The table of the number of acute migraine medication days per month in the DBT analysis period is provided, and summarizes the parameter descriptively as a continuous variable (including 2-sided normal 95% CIs for mean) by treatment group at each month of the DBT Phase and overall DBT mean.

### **Treatment Group Comparisons**

Treatment groups are compared using a model with the same properties as the model specified in Section 6.3.2.2, except that the number of acute migraine medication days per month is the dependent variable. The corresponding table has the same format. Results support exploratory objective #7.

## **6.4      Safety**

Safety parameters include the following: deaths; AEs; laboratory tests; vital signs; physical measurements; electrocardiograms (ECGs); and Columbia-Suicidality Severity Rating Scale (C-SSRS).

Tables of safety endpoints are provided according to safety analysis period and analysis set:

- On-DBT safety for the DBT safety analysis set by treatment group
- Post-DBT pre-OL rimegepant safety for the interim safety analysis set by treatment group and overall

- On-OL rimegepant safety for the OL rimegepant safety analysis set by treatment group/OL rimegepant and overall
- On-DB or OL rimegepant safety for the DB or OL rimegepant safety analysis set by treatment group/OL rimegepant and overall
- Follow-up safety for the follow-up safety analysis set by treatment group/OL rimegepant status and overall.

Results are presented by as-treated treatment group according to Section 6.1.1.1.

Measurements are slotted into analysis periods and analysis visits using the following steps:

- 1) Measurements are slotted into the pretreatment, on-treatment safety, and follow-up safety analysis periods.
- 2) Measurements are slotted into analysis visits in the analysis periods listed in the previous step (see Table 6). This does not apply to AEs.
- 3) Measurements in the on-treatment safety analysis period are slotted further into the on-DBT, post-DBT pre-OL rimegepant, and on-OL rimegepant safety analysis periods.

Refer also to the Core SAP for details about measurement slotting. See Sections 6.2.5, 7.2, and 7.3 for definitions of baseline, analysis periods, and analysis visit windows, respectively.

#### **6.4.1 Adverse Events**

Refer to the Core SAP for the following: AE start and end date imputation; death date derivation; counting and rounding rules in AE frequency tables; definitions of AEs related to study drug, significant AEs, and exposure-adjusted multiple occurrences of unique AEs; and TLF contents.

Frequency tables of AEs by SOC and PT display AEs in descending order of overall frequency within SOC and PT, unless otherwise specified.

The by-subject listing of AEs (i.e., non-SAEs and SAEs) is provided for the enrolled analysis set.

##### **6.4.1.1 Deaths**

Deaths are identified from any of the following sources:

- AE CRF with any of the following: PT or reported term of “death”; outcome of “fatal”; “yes” response to any death-related question (e.g., “Did the AE result in death?”; “Is a death certificate available?”; “Is an autopsy report available?”); complete or partially complete death date.
- DB Subject Status CRF with any of the following: death as reason for DBT Phase non-completion; death as reason for not continuing to the next phase (see Section 6.2.3.3)
- OLE Subject Status CRF with any of the following: death as reason for OLE Phase non-completion; death as reason for not continuing to the Follow-up Phase (see Section 6.2.3.4).

The by-subject listing of deaths is provided for the enrolled analysis set.

#### 6.4.1.2 AE Overviews

An AE overview frequency table displays the following categories without SOC and PT: any AE; AE related to study drug; AE leading to study drug discontinuation; SAE; SAE related to study drug; medication-overuse headache AE; hepatic-related AE; hepatic-related AE leading to study drug discontinuation; potential drug abuse AE; cardiovascular AE; suicidality AE; hypertension AE; and Raynaud's phenomenon AE.

AE overview frequency tables are provided for the following safety analysis periods and analysis sets:

- On-DBT for the DBT safety analysis set
- Post-DBT pre-OL rimegepant for the interim safety analysis set
- On-OL rimegepant for the OL rimegepant safety analysis set
- On-DB or OL rimegepant for the DB or OL rimegepant safety analysis set
- Follow-up for the follow-up safety analysis set.

#### 6.4.1.3 On-DBT AEs

Frequency tables of on-DBT AEs by SOC and PT are provided for the DBT safety analysis set for the following endpoints:

- AEs by worst intensity (other secondary objective #1)
- AEs related to study drug by worst intensity
- SAEs (other secondary objective #1)
- AEs leading to study drug discontinuation
- Hepatic-related AEs (exploratory objective #10)
- Hepatic-related AEs leading to study drug discontinuation (exploratory objective #10)
- Potential drug abuse AEs, displayed in alphabetical order by worst intensity and PT without SOC
- Cardiovascular AEs
- Suicidality AEs
- Hypertension AEs
- Hypertension AEs for subjects with medical history of hypertension.

Frequency tables of AEs by SOC and PT display AEs in descending order of rimegepant frequency within SOC and PT, unless otherwise specified.

#### 6.4.1.4 On-OL Rimegepant AEs

Frequency tables of on-OL rimegepant AEs are provided for the OL rimegepant safety analysis set by SOC and PT for the following endpoints:

- AEs by worst intensity (other secondary objective #1)
- AEs related to study drug by worst intensity
- SAEs (other secondary objective #1)
- AEs leading to study drug discontinuation
- Hepatic-related AEs (exploratory objective #10)
- Hepatic-related AEs leading to study drug discontinuation (exploratory objective #10)
- Potential drug abuse AEs, displayed in alphabetical order by worst intensity and PT without SOC
- Cardiovascular AEs
- Suicidality AEs
- Hypertension AEs
- Hypertension AEs for subjects with medical history of hypertension.

#### 6.4.1.5 On-DB or OL Rimegepant AEs

Frequency tables of on-DB or OL rimegepant AEs are provided for the DB or OL rimegepant safety analysis set by SOC and PT for the following endpoints:

- AEs by worst intensity (other secondary objective #1)
- SAEs (other secondary objective #1)
- Exposure-adjusted multiple occurrences of unique AEs.

Calculations for on-DB or OL rimegepant exposure-adjusted multiple occurrences of unique AEs use an analysis period reference start date = DB or OL rimegepant start date, analysis period reference end date = DB or OL rimegepant last date + 7 days if the DB or OL rimegepant last date is nonmissing, and analysis period reference end date = last contact date if the DB or OL rimegepant last date is missing.

#### 6.4.1.6 Follow-Up AEs

Frequency tables of follow-up AEs by SOC and PT are provided for the follow-up safety analysis set for the following endpoints:

- AEs by worst intensity
- SAEs.

## 6.4.2 Laboratory Tests

Laboratory tests are analyzed using results from local laboratory tests reported on CRFs and the external central laboratory Medpace. TLFs display results in both Systeme Internationale (SI) and United States (US) units, if applicable.

Laboratory tests of clinical interest are collected at the following visits:

- Hematology: Screening; Pre-Randomization; Weeks 12/EOT, 14, and 24/EOT
- Serum chemistry: Screening; Pre-Randomization; Weeks 12/EOT, 14, and 24/EOT.  
Exceptions are for the following:
  - LFTs (ALT, AST, alkaline phosphatase [ALP], TBL, direct bilirubin, indirect bilirubin):  
Screening; Pre-Randomization; Weeks 4, 12/EOT, 14, and 24/EOT.

The following by-subject laboratory test listings are provided for the enrolled analysis set:

- Laboratory test results using the Common Technical Criteria for Adverse Events/Division of Acquired Immune Deficiency Syndrome (CTCAE/DAIDS) toxicity grading scale (SI units). The listing displays all test results over time for subjects with grade 3 to 4 laboratory test abnormalities at any time point.
- Laboratory test results using the Food and Drug Administration (FDA) toxicity grading scale (US units). The listing displays all test results over time for subjects with grade 3 to 4 laboratory test abnormalities at any time point.
- LFT values and ratios to ULN (i.e., ALT, AST, TBL and ALP) (SI units). The listing displays all LFT results over time for subjects with select LFT elevations (ALT or AST > 3x ULN; ALP or TBL > 2x ULN) at any time point.
- Pregnancy test results (SI units). The listing displays all pregnancy test results over time for subjects with a positive pregnancy test at any time point.

Refer to the protocol for laboratory tests of clinical interest. Refer to the Core SAP for toxicity grades and TLF contents.

### 6.4.2.1 Laboratory Test Abnormalities

Frequency tables of the worst (highest) laboratory test abnormality for each graded laboratory test are provided for the following safety analysis periods and analysis sets:

- On-DBT for the DBT safety analysis set
- On-OL rimegepant for the OL rimegepant safety analysis set.

Grade 3 to 4 results support other secondary objective #1.

Frequency tables of laboratory test shift from baseline to the worst abnormality for each graded laboratory test are provided for the following safety analysis periods and analysis sets:

- On-DBT for the DBT safety analysis set

- On-OL rimegepant for the OL rimegepant safety analysis set

Separate tables are provided for each toxicity grading scale: CTCAE/DAIDS using SI units; and FDA using US units.

#### 6.4.2.2 LFT Elevations

Analyses use SI units.

#### **LFT Elevations**

Frequency tables of LFT elevations are provided for the following analysis periods and analysis sets:

- On-DBT for the DBT safety analysis set
- Post-DBT pre-OL rimegepant for the interim safety analysis set
- On-OL rimegepant for the OL rimegepant safety analysis set
- On-DB or OL rimegepant for the DB or OL rimegepant safety analysis set
- Follow-up for the follow-up safety analysis set.

#### Results support exploratory objective #11.

Frequency tables of LFT shift from baseline to the worst (highest) elevation are provided for the following safety analysis periods and analysis sets:

- On-DBT for the DBT safety analysis set
- On-OL rimegepant for the OL rimegepant safety analysis set.

#### **Exposure-Adjusted Cumulative LFT Elevations**

Frequency tables of exposure-adjusted cumulative LFT elevations are provided for the following safety analysis periods and analysis sets:

- On-DB or OL rimegepant for the DB or OL rimegepant safety analysis set.

Calculations use the same analysis period reference start and end dates as corresponding exposure-adjusted AEs (see Section 6.4.1.5).

#### **Time to First LFT Elevation**

Frequency tables of time to first LFT elevation are provided for the following safety analysis periods and analysis sets:

- On-DB or OL rimegepant for the DB or OL rimegepant safety analysis set with on-DB or OL rimegepant LFT elevations
  - Time categories are:  $\leq 2$ ,  $>2$  to  $\leq 4$ ,  $>4$  to  $\leq 8$ ,  $>8$  to  $\leq 12$ ,  $>12$  to  $\leq 16$ ,  $>16$  to  $\leq 20$ ,  $>20$  to  $\leq 24$ ,  $>24$  weeks.

- Time to elevation is calculated as (LFT collection date – DB or OL rimegepant start date + 1)/7.

## **LFT Plots**

Evaluation of drug-induced serious hepatotoxicity (eDISH) scatter plots are provided for the following safety analysis periods and analysis sets:

- On-DBT for the DBT safety analysis set by treatment group
- On-OL rimegepant for the OL rimegepant safety analysis set by treatment group/OL rimegepant.

By-subject LFT line plots are provided for the safety analysis set with select LFT elevations in any safety analysis period. Study weeks are defined as study day/7, where study day is derived from the laboratory test collection date (see Section 7.3). Each figure also displays DB study drug and OL rimegepant dosing days using symbols along the x-axis (see Section 9.5), and denotes additional study milestones (e.g., start of the on-DBT safety analysis period, start of the on-OL rimegepant safety analysis period, and start of the follow-up safety analysis period) using vertical lines with their corresponding descriptions in footnotes.

### **6.4.2.3 Laboratory Test Changes From Baseline Over Time**

The table of values and changes from baseline in all hematology and serum chemistry laboratory tests is provided by treatment group and overall for the safety analysis set at the following time points: baseline; each scheduled visit through Week 12 and EOT in the on-DBT safety analysis period; and each scheduled visit after Week 12 through Week 24 and EOT in the on-OL rimegepant safety analysis period. Results for overall are displayed only at baseline and time points in the on-OL rimegepant safety analysis period.

Note that scheduled visits vary according to laboratory test.

A separate table is provided for each unit system (SI or US).

Refer to the Core SAP for (1) handling multiple values in an analysis visit window or on the same laboratory test collection date, and (2) deriving the EOT value in an on-treatment safety analysis period.

### **6.4.3 Vital Signs and Physical Measurements**

Vital signs include systolic blood pressure, diastolic blood pressure, heart rate, temperature, and respiratory rate. Physical measurements include height, weight, and body mass index (BMI). These parameters are measured at all visits except Pre-Randomization Evaluation, and height is measured only at the Screening Visit.

Refer to the Core SAP for TLF contents.

#### **6.4.3.1      *Vital Sign and Physical Measurement Changes From Baseline Over Time***

The table of values and changes from baseline in vital sign and physical measurement parameters is provided by treatment group and overall for the safety analysis set at the following time points: baseline; each scheduled visit through Week 12 and EOT in the on-DBT safety analysis period; each scheduled visit after Week 12 through Week 24 and EOT in the on-OL rimegepant safety analysis period; and Follow-Up Week 2 in the follow-up safety analysis period. Results for overall are displayed only at baseline and time points during the on-OL rimegepant and follow-up safety analysis periods.

The table of values and changes from baseline in vital sign parameters is also provided for the safety analysis set with medical history of hypertension.

Refer to the Core SAP for (1) handling multiple values in an analysis visit window or on the same measurement date, and (2) deriving the EOT value in an on-treatment safety analysis period.

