4.3.4. Open-label Extension (OLE) Phase

It is estimated that approximately 480 patients will be entered into the open-label extension phase.

The OLE Phase will be up to 12 weeks and will have scheduled visits at Week 14 and Week 24/ OLE EOT. See [Table 2](#) for schedule of assessments.

Scheduled every other day (EOD) dosing with open-label study drug (regardless of migraine status) should be continued throughout the entire course of the OLE Phase.

Day 1 of the OLE Phase is defined as Week 12 visit date plus 1 calendar day.

Dosing with open-label study drug (rimegepant 75mg ODT) should BEGIN two calendar days after the final scheduled dosing day for blinded study drug, to maintain the EOD dosing schedule throughout the entire course of the trial (DBT and OLE Phases).

Subjects who discontinue early from the DBT Phase or have already entered the Follow-up Phase are not eligible to enter the OLE Phase. Subjects who discontinue who are otherwise not eligible for the OLE Phase, per the discretion of the Investigator, in consultation with the Medical Monitor, should enter the Follow-up Phase. Subjects who successfully complete the DBT Phase, and have not completed the Follow-up Week 2 Visit, may enter the OLE Phase, at the discretion of the Investigator.

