4.3.5. Follow-up Phase

All randomized subjects should complete the Follow-up Week 2 Visit, except those who discontinue early from the study due to withdrawal of consent, loss of a subject's ability to consent freely, death, or when a subject is lost to follow-up.

The Follow-up Phase will have one scheduled visit at Follow-up Week 2 for targeted safety assessment and end-of-study procedures. At this visit, subjects will undergo the follow-up visit procedures as detailed in Table 1 for those subjects that either discontinue early from the DBT Phase or do not enter the OLE Phase, and Table 2 for those subjects completing or discontinuing early from the OLE Phase. In addition, compliance with the concomitant medication paper diary will be assessed. Investigators should assess subjects for AEs consistent with drug dependency or withdrawal effects and report as appropriate (see Section 7.4).

The Follow-up Week 2 Visit is to occur approximately 2 weeks (14 days +/- 2 days) after the last visit in the last treatment phase (i.e., Week 12/DBT EOT Visit if the subject did not enter the OLE Phase; Week 24/OLE EOT Visit if the subject entered the OLE Phase).

Subjects will continue to record all concomitant medications, including standard of care acute migraine medications (both prescribed and OTC), taken during the Follow-up Phase in the Concomitant Medication paper diary.

Due to the COVID-19 Pandemic, some selected study visits may be conducted remotely (Ex: Telephone, telemedicine) and must be documented within the source records as being conducted remotely. All procedures not able to be completed due to a visit being conducted

remotely must be reported as a protocol deviation and can be performed at the next visit, where appropriate to do so based on subject participation.

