**Table 5 Treatment Group Presentation in Tables by Analysis Set**

Analysis Set	Number of Columns	Abbreviated Treatment Group
Enrolled	1	Overall
Full, DBT efficacy, migraine, safety, DBT safety, interim safety by treatment group and {overall}	2 to 3	Rimegepant 75 mg Placebo {Overall}
OL rimegepant safety, DB or OL rimegepant safety by treatment group/OL rimegepant and overall	3	DB RMG/OL RMG DB PBO/OL RMG Overall
Follow-up safety by treatment group/OL rimegepant status and overall	5	DB RMG/OL RMG DB PBO DB PBO to OL RMG DB PBO No OL RMG Overall

Results for study population also include overall treatment group (see [Section 6.2](#)).

Subgroup tables of efficacy endpoints have the same format as the main efficacy tables, but display each subgroup level in a separate row, and page break by subgroup level. A separate table is produced for each efficacy subgroup of interest.

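### The Follow-Up Week 2 row of the vital-sign change table pools placebo subjects who took open-label rimegepant with those who never did, contrary to the SAP's own follow-up column rule (minor)

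*SAP*

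**What the plan says.** SAP 6.4.3.1 defines one table of values and changes from baseline in vital signs and physical measurements. It "is provided by treatment group and overall for the safety analysis set at the following time points": baseline, the visits through Week 12, the later visits through Week 24, "and Follow-Up Week 2 in the follow-up safety analysis period". It adds that "Results for overall are displayed only at baseline and time points during the on-OL rimegepant and follow-up safety analysis periods". A second sentence asks for the vital-sign table again in subjects with a history of hypertension, naming the same analysis set and no other layout.

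Table 5 gives safety-set tables two or three columns: Rimegepant 75 mg, Placebo and, where used, Overall. It has a separate row headed "Follow-up safety by treatment group/OL rimegepant status and overall", with five columns: DB RMG/OL RMG; DB PBO; DB PBO to OL RMG; DB PBO No OL RMG; Overall. The general rule in SAP 6.4 agrees: "Follow-up safety for the follow-up safety analysis set by treatment group/OL rimegepant status and overall". SAP 6.1.1.1 lets later sections state exceptions. Section 6.4.3.1 neither describes its follow-up row as an exception nor gives a reason for one.

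On timing, Protocol 4.3.5 places the single follow-up visit about 2 weeks after the last visit of the last treatment phase. That is the Week 12/DBT EOT Visit for subjects who do not enter the extension, and the "Week 24/OLE EOT Visit if the subject entered the OLE Phase". On numbers, Protocol 4.3.4 estimates that "approximately 480 patients will be entered into the open-label extension phase".

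**The concern.** At every other row of this table the content of the Placebo column is clear. Through Week 12 it holds subjects on placebo. At Weeks 14 and 24 the analysis period itself shows that everyone is on open-label rimegepant. Follow-Up Week 2 is the one row where the column mixes two exposure histories and two calendar positions, and neither the row label nor the column label says so. The Overall column pools further and does not help.

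At stake is whether a reader of the LSLV report can tell whose blood pressure, heart rate and weight after stopping drug are being summarized. A column headed Placebo beside one headed Rimegepant 75 mg invites reading as unexposed against exposed, when most of the Placebo column would have had recent exposure.

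**Working it through.** **Column rules side by side**

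| Source | Analysis set | Placebo subjects at follow-up |
|---|---|---|
| SAP 6.4.3.1 with Table 5, safety row | Safety | One column, Placebo |
| SAP 6.4 with Table 5, follow-up row | Follow-up safety | DB PBO, plus DB PBO to OL RMG and DB PBO No OL RMG |
| SAP 6.4.3.2, follow-up abnormalities | Follow-up safety | Split, by the Table 5 follow-up row |

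The laboratory (6.4.2.3) and ECG (6.4.4.1) change tables have no follow-up row, so among the change tables the issue is confined to vital signs and physical measurements. For subjects with a history of hypertension, 6.4.3.2 lists abnormality tables on double-blind and on open-label treatment only. The 6.4.3.1 table is therefore the only vital-sign summary for them that can reach follow-up. I read its time points as those of the main table, because none are restated.

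**Timing**

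- Extension completers: Week 24 + 2 = about Week 26.
- Double-blind completers who do not enter the extension: Week 12 + 2 = about Week 14.
- Gap: 26 − 14 = about 12 weeks. Early discontinuers in either phase are seen sooner.

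**Size**

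Inputs: about 600 randomized 1:1, so 300 on placebo (protocol synopsis and 5.1); about 480 entering the extension, both arms combined (Protocol 4.3.4). The 480 is a planning estimate without a derivation, so only the ratio can be formed.

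- Entry share: 480/600 = 80%.
- Placebo subjects exposed to open-label rimegepant, equal entry by arm assumed: 0.80 × 300 = 240.
- Placebo subjects never exposed: 300 − 240 = 60.

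Attendance at Follow-Up Week 2 is not given. Assume 95% of entrants and 50% to 95% of non-entrants attend.

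- Exposed with a visit: 240 × 0.95 = 228.
- Never exposed with a visit: 60 × 0.50 = 30 to 60 × 0.95 = 57.
- Exposed share of the column: 228/(228 + 57) = 80.0% to 228/(228 + 30) = 88.4%.

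Varying placebo-arm entry under the same attendance assumptions:

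| Placebo-arm entry | Never exposed with a visit | Exposed share of column |
|---|---|---|
| 60% | 60 to 114 | 60.0% to 74.0% |
| 70% | 45 to 86 | 70.0% to 81.6% |
| 80% | 30 to 57 | 80.0% to 88.4% |
| 90% | 15 to 28 | 90.0% to 94.5% |

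The 60% row is the floor if 480 enter in total and all 300 rimegepant subjects are among them: (480 − 300)/300 = 180/300. Even there, exposed subjects form the majority of the column.

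**The case against.** The strongest reply is that little depends on this row. Protocol 9.3.2 treats safety endpoints descriptively, and 6.4.3.1 asks for no between-group difference, interval or test. A reader might infer that a planned off-drug comparison with placebo is spoiled; no such comparison is planned. SAP 8.1 limits over-time tables in the PCD report to pretreatment and the double-blind phase, so the row appears only in the LSLV report. Follow-up abnormalities in 6.4.3.2 are already split. All of this stands, and it sets the severity. It does not cover mean changes, or any follow-up vital-sign summary in the hypertension-history subgroup.

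A second reply is that the Week 14 and Week 24 rows already require the Placebo heading to be read as the original double-blind group. That is fair for those rows, where every subject shares one current treatment. It does not carry over to a row that mixes exposed and never-exposed subjects.

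Third, SAP 6.4.3 defers output contents to the Core SAP, and 6.1.1 places templates in a mock document. Neither is available here, and either could alter the columns or add a footnote. But 6.4.3.1 itself names the analysis set and the grouping, so this text needs correcting or cross-referencing in any case.

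Fourth, splitting the columns does not create a fair control. The never-exposed group consists of double-blind discontinuers and others who did not enter the extension, seen about 12 weeks before extension completers. That also stands, and the fix should say so.

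**Conclusion.** The inconsistency is real and minor. Followed as written, 6.4.3.1 departs without explanation from the SAP's rule for follow-up safety, and about 80% of the Placebo column at Follow-Up Week 2 would have taken open-label rimegepant. That figure rests on a both-arms planning estimate, equal entry by arm, and similar visit attendance by entrants and non-entrants; the denominator of 300 also ignores any randomized subjects who were never dosed.

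Four stronger readings are not supported:

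- That almost no unexposed placebo subjects exist. About 60 are expected before visit losses; they are pooled, not absent.
- That 80% have completed 12 weeks of open-label drug. The estimate counts entry into a phase of up to 12 weeks.
- That the table would show only one fifth of a true exposed-versus-unexposed difference. This needs entrants and non-entrants to be exchangeable, Week 14 and Week 26 values to be interchangeable, and all exposed subjects to share one effect. The documents support none of these.
- That the hypertension-history subgroup was added to study effects after stopping. SAP 4.3 defines it for hypertension-related endpoints in the double-blind and open-label safety sets.

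**What to change.** In SAP 6.4.3.1, take Follow-Up Week 2 out of the safety-set table. Present its values and changes for the follow-up safety analysis set with all five Table 5 follow-up columns: DB RMG/OL RMG; DB PBO; DB PBO to OL RMG; DB PBO No OL RMG; Overall. Do the same for the hypertension-history table, and state its time points explicitly.

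Add a footnote that DB PBO No OL RMG is a selected, non-randomized group measured earlier than subjects who completed the extension. The split then corrects the labelling without suggesting an unbiased off-drug contrast. Check the Core SAP and the mock outputs for the same layout.

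The cost is a wording change and two re-columned outputs for the LSLV report, using data, analysis sets and column definitions that the SAP already has.
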